8.7. Genetics

Unpleasant reactions to alcohol consumption in humans with naturally occurring *ALDH2* mutations are thought to be protective against AUD and account for its low prevalence in individuals who are heterozygous or homozygous for *ALDH2* allele mutations. A 6 mL sample of whole blood for DNA isolation will be collected from participants who have consented to *ALDH2* genotyping. Participation is optional; participants who do not wish to undergo genotyping may still participate in the study.

In the event of DNA extraction failure, a replacement genetic blood sample may be requested from the participant. Signed informed consent will be required to obtain a replacement sample, unless it was included in the original consent.

See [Section 10.5](#) for information regarding the use of DNA samples. Details on processes for collection and shipment and destruction of these samples can be found in the Laboratory Manual.

8.8. Immunogenicity Assessments

Serum samples for the detection and characterization of antibodies to DCR-AUD will be stored until a validated assay method is available.

Serum samples will be collected at times specified in the SoA ([Section 1.3](#)). Additionally, serum samples should also be collected at the final visit from participants who discontinued study intervention or were withdrawn from the study.

Serum samples will be screened for antibodies binding to DCR-AUD, and the titer of confirmed positive samples will be reported. Other analyses may be performed to verify the stability of antibodies to DCR-AUD and/or further characterize the immunogenicity of DCR-AUD.

Antibodies may be further characterized and/or evaluated for their ability to neutralize the activity of DCR-AUD.

8.9. Health Economics

Health Economics parameters are not planned for this study.

9. STATISTICAL CONSIDERATIONS

9.1. Statistical Hypotheses

Statistics will be descriptive. No tests of statistical inference are planned.

9.2. Sample Size Determination

No formal sample size estimations were performed. The sample size of 16 participants (12 active and 4 placebo) was considered sufficient to provide an initial assessment of the safety profile of DCR-AUD in HVs, and adequate for the purpose of describing PK/PD data in HVs.

The sample size is based on clinical rather than statistical considerations.

9.3. Populations for Analyses

For purposes of analysis, the following populations are defined.

Population	Description
Enrolled	All participants who sign the ICF.
Randomized	All participants who sign the ICF and who are randomized to study intervention.
Pharmacokinetic	All participants randomized to study intervention and who receive at least 1 dose of DCR-AUD and have at least 1 postdose PK assessment.
Pharmacodynamic	All participants randomized to study intervention and who receive at least 1 dose of DCR-AUD or placebo and have at least 1 postdose PD assessment
Safety	All participants randomized to study intervention and who receive at least 1 dose of DCR-AUD or placebo. Participants will be analyzed according to the initial dose received.

9.4. Statistical Analyses

The statistical analysis plan (SAP) will be finalized prior to database lock. The SAP will include a more technical and detailed description of the statistical analyses described in this section. This section is a summary of the planned statistical analyses of the most important endpoints including primary and key secondary endpoints.

9.4.1. General Considerations

In general, summary statistics (n, mean, SD, median, minimum, and maximum for continuous variables, and number and percentage of participants in each category for categorical variables) will be provided for all variables.

Baseline is defined as the last non-missing measurement prior to the date and time of the dose of study intervention.

All analyses will be based on observed data without imputation for missing values. Except for outlier analyses, measurements collected from unscheduled visits will not be included in the summary tables or figures but will be included in the participant listings. Source data for the summary tables and statistical analyses will be presented as participant data listings.

9.4.2. Primary Endpoint(s)

The primary endpoints of the study are the assessment of the incidence and severity of AEs and SAEs, and the changes from baseline in vital signs, 12-lead ECG, clinical laboratory tests, and physical examination findings.

All safety analyses will be performed on the Safety Population. Adverse events will be defined as treatment-emergent AEs if they have a start date on or after the administration of study intervention during the treatment period. Frequency and percentages by treatment group will be used to summarize AEs, SAEs, AEs of special interest, and AEs by relationship.

Descriptive statistics and changes from baseline will be provided for vital signs, 12-lead ECG, clinical laboratory tests, and physical examination findings by treatment group and visit.

Laboratory parameter shifts from baseline to abnormal post-baseline values will be presented by treatment group. Mean laboratory values over time will be plotted by dose group.

By-participant listings will be provided for all the safety parameters.

9.4.3. Secondary Endpoints

PD analyses will be performed on the Pharmacodynamic Population, and PK analyses will be performed on Pharmacokinetic Population. Actual sampling times will be used for all parameter estimations. The principal secondary endpoint of interest will be the change from baseline in the composite 6-symptom score after EIAs (as described in [Section 8.6.1.2](#)).

9.4.3.1. EIA Composite Score

EIAs will include an active assessment of the 6 key symptoms (flushing, headache, palpitations, lightheadedness, nausea, and vomiting) that DCR-AUD may elicit, in order to determine if the protocol-specified DCR-AUD dose regimen gives the proper constellation of these symptoms. These symptoms will be collected by active questioning of each participant at different time points during each EIA.

The following symptom scoring framework would be described as an arbitrary point system, where:

Symptom	No Symptom	Mild symptom	Moderate symptom	Severe symptom
Score	0	1	2	3

Each participant at each timepoint in an EIA after alcohol administration will be given a composite score for that timepoint as sum of all 6 symptom scores.

Baseline is defined as last non-missing value prior to alcohol administration.

Descriptive statistics of EIA composite score (n, mean, median, IQR [Inter Quartile Range], minimum and maximum) for absolute values and changes from baseline will be presented by treatment, placebo, visit, and time point.

Descriptive statistics of Peak EIA composite score (n, mean, median, IQR, minimum and maximum) for absolute values and changes from baseline will be presented by treatment, placebo, and visit (Days). The Peak EIA composite score is defined as maximum composite score at each visit.

9.4.3.2. Blood Biomarkers

Descriptive statistics and change from baseline will be provided for blood PD assessments, including acetaldehyde accumulation (absolute values and AUC) during the EIAs, where applicable.

9.4.3.3. Pharmacokinetics

Plasma concentrations and PK parameters will be listed and summarized by group and by time point with descriptive statistics. The arithmetic mean, SD, CV%, geometric mean, geometric CV%, minimum, median, and maximum will be presented.

Additional PK parameters may be estimated if deemed appropriate. Details will be provided in the PK Analysis Plan. Analysis of PK parameters may be reported in a supplement to the CSR.

PK analyses will be conducted with noncompartmental and/or compartmental models to determine PK parameter estimates. Population PK and Population PK-PD analyses may be performed and will be reported in a separate report.

9.4.4. Exploratory Endpoint(s)

The exploratory endpoint of change in drinking amounts will be assessed using the TLFB and by analysis of blood levels of phosphatidylethanol.

Average daily drinking amounts over each 2-week period after the start of dosing will be compared to the amount during the 2-week period before first dose. Change in drinking amounts for each postdose period will be evaluated in connection with changes in EIA-induced peak symptoms and plasma acetaldehyde levels during the preceding EIA.

Other exploratory analyses will be conducted as deemed appropriate and will be detailed in the SAP.

9.5. Interim Analysis

In order to enable decision making for the future clinical development of DCR-AUD, an interim analysis may be conducted after all participants have received all 3 doses of study intervention.

Variables to be analyzed may include assessments of safety (AEs, laboratory testing, physical findings), pharmacokinetics, and pharmacodynamics (blood biomarkers and physiologic signs and symptoms). Should the interim analysis be conducted, complete details will be provided in the SAP.

9.6. Safety Review Committee and Data Safety Monitoring Committee

An SRC will conduct periodic reviews and will review all cumulative safety, tolerability, and available PD data on participants. Participant safety will be continuously monitored by the SRC by ongoing review of AEs, laboratory results, and other protocol-specified assessments, to allow safety signal detection throughout the study.

Table 5 shows the minimal required timing of reviews by the SRC, as well as the decisions that the SRC may undertake with respect to the possible occurrence of study stopping rules (see Section 7.4).

At its discretion, and based on clinical judgment, the SRC may suspend DCR-AUD dosing or EIAs during the study at any time, even for reasons not explicitly stated elsewhere, and refer to the DSMC for any potential concern regarding participant safety or wellbeing. In addition, the DSMC will be convened on an ad hoc basis if an AE does trigger a stopping rule. The DSMC will review data and advise on whether the study should be stopped to ensure the safety of study participants.

Complete details on the responsibilities of the Safety Committees will be detailed in the committee charters. For additional details on the composition of the SRC and DSMC, refer to [Section 10.1.5](#).

Table 5: Minimal Timing of the Safety Review Committee Data Reviews

Occurrence of a significant or severe adverse symptom	Upon the occurrence of a significant or severe adverse symptom (see Section 7.3), all dosing and enrollment into the study will be interrupted until safety data can be reviewed by the SRC. The SRC will review the events associated with the significant or severe adverse symptom as well as the cumulative safety data collected on all participants previously dosed. The SRC will determine whether dosing, enrollment, and subsequent EIAs may resume.
Occurrence of a safety issue that, in the SRC's clinical judgment, could affect participant safety or study conduct	Upon the occurrence of a situation or safety question that could affect participant safety or study conduct, the SRC will meet to discuss the issue. Actions to be taken include, but are not limited to: 
 • Discontinuation of an individual participant • Discontinuation of dosing • Discontinuation of additional EIAs • Referral to the DSMC for review and recommendation, should a pattern of AEs of concern be identified, regardless of severity
Occurrence of a potential study stopping rule	Upon the occurrence of a potential study stopping rule (see Section 7.4), all dosing and enrollment will be interrupted until safety data can be reviewed by the SRC. The SRC will review the events associated with the triggering of the stopping rule as well as the cumulative safety data collected on all participants previously dosed. The SRC will determine whether dosing and enrollment may resume. The SRC may elect to refer the issue that triggered the study interruption to the DSMC for an independent review and recommendation regarding study resumption.

Abbreviations: AE: adverse event; AUD: alcohol use disorder; DSMC: Data Safety Monitoring Committee; EIA: ethanol interaction assessment; SRC: Safety Review Committee

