7.3. Individual Participant Stopping Rules

7.3.1. Serious Adverse Event

If a participant experiences an SAE ([Section 10.3.2](#)), unless it is clearly the result of a non-study-related event, further dosing of the participant will be paused while the SRC reviews the event. Based on this review, a decision will be made as to whether the participant may continue to receive doses of study intervention. In participants who have completed dosing, continued follow-up with protocol-specified assessments, including subsequent EIAs, will be pursued if the participant is willing and the PI determines it is safe to do so. Additional EIAs will not be performed if, in the clinical judgment of the PI and/or SRC, the SAE could be related to study intervention and that repeat EIAs pose a recurrent risk to the participant, or if the participant declines these additional assessments. Participants will continue to be followed for other study procedures as detailed in the SoA.

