7.3.4. Significant Negative Reaction to Alcohol Ingestion

Any participant who experiences a significant negative reaction to alcohol ingestion that includes severe or serial vomiting or hemodynamic instability (syncope or significant pre-syncope, or BP decline of more than 25 mmHg from Baseline with some lightheaded symptoms, or HR increases to ≥ 110 bpm with some symptoms during an EIA) will be discontinued from additional dosing and will be advised to not drink outside of the clinic for the duration of the study. The participant will continue to be followed in the study for other protocol-specified procedures. The PI will determine if additional/subsequent protocol-specified EIAs will be conducted, based on the nature and severity of symptoms observed.

See [Section 8.6.1.3](#) regarding full details on stopping rules for conduct of an EIA.

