10.6. Liver Safety: Suggested Actions and Follow-up Assessments

Phase 1 liver chemistry stopping criteria are designed to ensure participant safety and to evaluate liver event etiology:

Liver Chemistry Stopping Criteria (Applies both to additional DCR-AUD dosing and further EIAs)	
ALT/AST-absolute	
ALT or AST increases to $\geq 3 \times \text{ULN}$
 
If ALT or AST \geq increases to $>2 \times \text{ULN}$ AND total bilirubin $\geq 2 \times \text{ULN}$ ($> 35\%$ direct bilirubin) or INR > 1.5, report to Sponsor in expedited manner.^{a, b}
 
See additional actions and follow-up assessments below

^a Serum bilirubin fractionation should be performed if testing is available. If serum bilirubin fractionation is not immediately available, discontinue study intervention if ALT $\geq 3 \times \text{ULN}$ and total bilirubin $\geq 2 \times \text{ULN}$.

Additionally, if serum bilirubin fractionation testing is unavailable, record the absence/presence of detectable urinary bilirubin on dipstick which is indicative of direct bilirubin elevations suggesting liver injury.

^b All events of ALT $\geq 3 \times \text{ULN}$ and total bilirubin $\geq 2 \times \text{ULN}$ ($> 35\%$ direct bilirubin) or ALT $\geq 3 \times \text{ULN}$ and INR > 1.5 may indicate severe liver injury (possible 'Hy's Law') and must be reported to sponsor in an expedited manner and as an SAE if SAE criteria met (excluding studies of hepatic impairment or cirrhosis).

Required Actions, Monitoring, and Follow-up Assessments	
Actions:	
 Immediately discontinue study intervention Report the event to the CRO Medical Monitor within 24 hours Complete an SAE data collection tool if the event also met the criteria for an SAE^b Perform liver function follow-up assessments as described in the Follow Up Assessments below. Do not restart or rechallenge participant with study intervention (neither IMP nor additional EIAs). Monitor the participant until liver function test abnormalities resolve, stabilize, or return to baseline (as detailed below).

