4.13.9 Safety Review Committee

A Safety Review Committee (SRC) will conduct periodic reviews and will review all cumulative safety, tolerability, and available PD data on participants, approximately every month or every 3 weeks during treatment and post dose follow-up. Participant safety will be continuously monitored by the SRC by ongoing review of AEs, laboratory results, and other protocol-specified assessments, to allow safety signal detection throughout the study.

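### Table 5's automatic hold after a significant or severe adverse symptom leaves out the EIAs, and Sections 9.6 and 7.4 disagree on whether the DSMC must be convened

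*Protocol*

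**What the plan says.** Table 5 in Protocol Section 9.6 sets the minimum timing of SRC reviews.

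- **Row 1** (significant or severe adverse symptom, with a pointer to Section 7.3). The hold is: "all dosing and enrollment into the study will be interrupted until safety data can be reviewed by the SRC". The release is: "The SRC will determine whether dosing, enrollment, and subsequent EIAs may resume".
- **Row 2** (a safety issue in the SRC's judgment). One action open to the SRC is "Discontinuation of additional EIAs".
- **Row 3** (potential study stopping rule). Both the hold and the release name dosing and enrolment only. Referral to the DSMC is at the SRC's option.

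The text of 9.6 adds that, on clinical judgment, "the SRC may suspend DCR-AUD dosing or EIAs during the study at any time". It also makes an ad hoc DSMC meeting mandatory if an AE triggers a stopping rule.

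Section 7.4 has two sets of stopping rules, both conditional on an SRC recommendation. The CTCAE-grade rules stop dosing. The alcohol-symptom rule (three DCR-AUD participants) stops dosing and EIAs. After a trigger and an SRC halt, 7.4 lets the SRC ask for a DSMC review but does not require it.

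For the participant who reacts, Section 7.3.4 stops further dosing and says: "The PI will determine if additional/subsequent protocol-specified EIAs will be conducted, based on the nature and severity of symptoms observed".

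**The concern.** Row 1 releases something that it never held. Either the EIAs were meant to be paused and the word is missing, or the release clause is wrong. A site acting on the hold sentence alone would stop injections and enrolment and carry on giving ethanol to everyone else.

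That matters because ethanol is the exposure that provokes the reaction. Section 4.2 expects that symptoms may need repeat doses and several months to appear. They may therefore first appear after dosing has ended, when a dosing hold has nothing to act on.

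The DSMC wording raises a second question. The SRC consists of the PI and/or a sub-investigator and two medical monitors (10.1.5.1). The DSMC is the only independent data committee. Whether it meets after a stopping rule is triggered should not depend on which section is read.

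**Working it through.** The plan gives no figure to reproduce. The check is a comparison of wording and a count from the schedules.

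**1. Does dosing include EIAs?** The protocol usually names the two separately.

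- Section 7.3.1, on an SAE: "further dosing of the participant will be paused while the SRC reviews the event". EIAs are dealt with in later sentences of that section.
- Section 10.6, on liver criteria: "Applies both to additional DCR-AUD dosing and further EIAs".
- Section 7.4 and the risk table in 2.2.2 name dosing and EIAs side by side for the alcohol-symptom rule.
- Row 1 itself lists dosing and EIAs as separate items in its release clause.

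A site therefore has no firm basis for reading EIAs into the hold sentence.

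**2. When does the written hold have nothing to pause?**

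- Dosing days (4.1): 1, 29, 57.
- EIA days from Table 1: -1, 28, 56, 168. Some sections call the last one Day 169, which does not affect the count.
- EIA days from Table 2: 14, 42, 70, 84, then Weeks 16 and 20, taken here as Days 112 and 140 because those column entries are not legible. Both are after Day 57 on any reading.
- Total: 4 + 6 = 10, matching Table 1 footnote n.
- After the first dose: 10 − 1 = 9.
- After Day 57: 70, 84, 112, 140, 168 = 5.
- Share: 5/9 = 56%.
- For the 12 DCR-AUD participants with full attendance: 5 × 12 = 60 of 9 × 12 = 108 planned post-dose EIAs.

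This shows how much of the schedule lies beyond the reach of a dosing hold. It does not count EIAs that would take place while a hold is in force.

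**3. Row 3 against 7.4.** Row 3 holds and releases dosing and enrolment. The CTCAE rules stop dosing, so row 3 matches them. The alcohol-symptom rule also stops EIAs, so for that one trigger the interim hold is narrower than the stop it precedes.

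**4. DSMC: 9.6 against 7.4.** The triggers are not worded identically. Section 9.6 needs an AE that triggers a rule. Section 7.4 needs a triggered rule and an SRC halt. They overlap when a CTCAE event (one at Grade 4 or above, or Grade 3 in two participants) meets a 7.4 rule and the SRC halts dosing. There, 9.6 requires the DSMC and 7.4 makes it optional, which is a direct conflict.

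The 9.6 sentence is also slightly too narrow. Under 10.3.1, symptoms elicited by questioning during an EIA are not AEs. An alcohol-symptom trigger resting only on such symptoms would fall outside it. Spontaneously reported events and clinically significant vital-sign changes are AEs and fall within it.

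**The case against.** The best reply is that row 1 already implies an EIA pause, since an activity can restart only if it was stopped and the clause is in the same cell. Section 10.6 gives some support, because its no-rechallenge instruction groups the drug and the EIAs together. This is probably what the sponsor intended. It supports adding the word, but does not make the hold sentence say it.

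The other safeguards are substantial:

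- Section 8.6.1.3 allows ethanol to be stopped within any EIA for vomiting, blood pressure, heart rate or temperature changes, or clinical judgment. This protects other participants too.
- EIAs are closely observed, with four aliquots over 80 minutes and an overnight stay.
- Section 7.3.4 covers the participant who reacted.
- The SRC monitors continuously, includes site leadership, and can suspend EIAs at any time. Some sponsor staff are unblinded for safety.

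All of this stands and lowers the stakes. None of it is an automatic pause for other participants. Section 8.6.1.3 acts only once an EIA is under way, and the SRC's power is discretionary. The committee charters were not available. They may add detail but cannot reconcile two sections of the protocol.

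There is also a scientific objection. The symptoms are the intended pharmacodynamic signal, and 7.3.4 can be met by a heart rate of 110 bpm with some symptoms during an EIA, possibly on placebo. A study-wide pause therefore has a real price, taken up under the fix.

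Three stronger readings are tempting but not supported:

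- A reader might set the SAP's review interval (4.13.9), "approximately every month or every 3 weeks during treatment and post dose follow-up", against the EIA spacing and infer how many EIAs would run during a hold. Row 1's review is triggered by the event and has no stated time limit, so the routine interval does not measure it.
- A reader might call the DSMC the only independent reviewer. The IRB/IEC must also be told of SAEs and significant safety findings (10.1.1).
- A reader might count row 3's optional referral as a further DSMC conflict. It concerns a potential stopping rule and can coexist with mandatory convening once a rule is triggered.

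**Conclusion.** The point holds as a wording defect in a safety instruction, and it should be fixed. Row 1's automatic hold omits the EIAs that its release clause presupposes. Read literally, it leaves other participants' challenges running until the SRC acts. For anyone past the Day 57 dose it pauses nothing, with 5 of 9 post-dose EIAs (56%) in that period. Row 3 has the same gap for the alcohol-symptom rule only. Sections 9.6 and 7.4 conflict on the DSMC for a CTCAE event that triggers a rule and leads to an SRC halt.

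The 5 of 9 assumes the planned schedule, with Weeks 16 and 20 placed after Day 57. The conclusion also assumes that sites follow the hold sentence as written. It does not say that participants would be unprotected, and the documents give no basis for estimating how many EIAs would proceed during a review.

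**What to change.** - **Table 5, row 1:** add EIAs to the hold, so that dosing, enrolment and EIAs are all interrupted until the SRC has reviewed the safety data. The release clause then matches.
- **Table 5, row 3:** add EIAs to the hold and release clauses when the trigger is the alcohol-symptom rule of 7.4.
- **Sections 9.6 and 7.4:** state one DSMC rule in both. Either choice removes the conflict. The mandatory wording of 9.6 is the safer one and should be extended from an AE to any 7.4 stopping rule.

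The cost is a few words in Table 5, 7.4 and 9.6 and matching charter text, with no extra participants or procedures. The downside is that one event, possibly in a placebo participant, may delay or lose some EIAs until the SRC meets, which thins the onset and waning profile. Visit windows (±2 to ±3 days where legible in Table 2) and the option in 8.6.1 to make up a missed EIA soften this.
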